### **D1. 3. Statistical Analysis:**

Due to the nature of 3+3 design (**Figure 4**), the theoretical sample size varies from 3 to 36 depends on when the trial stops under "stopping rule". However, we hypothesize that no major responses will occur at any current (dose) level and the current will be escalate to 4 mA, thus we predict that 18 stroke subjects will be required for Aim 1. First, patients' demographic and clinical characteristics will be summarized. Summary statistics for continuous variables includes number of subjects, means, median and standard deviations. Summary statistics for discrete variables includes counts and percentages for each category. Secondly, the safety measures will be summarized by current(dose) group with descriptive statistics. Thirdly, a current(dose) response curve will be plotted by MEPs amplitude versus current (dose) groups. Per DSMB recommendation, S-100 and NSE will not used as a stopping rule, however, they will be still collected and analysed separately and presented to DSMB meeting. The statistical analyses will be performed with SAS V9.2 (SAS Institute Inc., Cary NC).

### **D1. 4. Anticipated Results:**

We anticipate that 4.0 mA will be tolerable and safe both at clinical and subclinical levels, as evidenced by a lack of major responses in the study subjects. In addition we expect that 4.0 mA will produce the largest increase in MEPs amplitude compared with other current levels.

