#### Aim 1: To determine the optimal current in stroke patients

##### D1.1 Design:

This aim is a phase I type study to determine the most efficacious current for tDCS, recognizing that this current level must be tolerable and safe. The trial design is adapted from the classical, gold-standard 3+3 drug trial design, which is commonly used to find the maximal tolerable dose for a chemical drug. The main justification for this design is that the maximal tolerable current (dose) is usually and arbitrarily defined as the dose at which one-third of the patients experience current (dose)-limiting major side effects/response. The algorithm for current (dose) escalation is detailed in (**Figure 4**). The study starts with 1 mA : (a) if no major response occurs in any of the three subjects, a next current at 2 mA will be used next; (b) if major response occurs in 2-3 study subjects, then the trial will stop at this current level; (c) if major response occurs in one subject, then 3 additional study subjects will be entered to further test the safety of same current dose; if no major response occurs, then the current will be escalated next current level; if further major response occurs, then the trial will terminate. The previous current level will be defined as the maximal tolerable current (dose). The current tDCS device available on the market (Chattanooga Dual-Channel Iontophoresis Device) for research use has a maximal current of 4.0 mA. The sequence for current escalation will be 1.0 mA >> 2.0 mA >> 2.5 mA >> 3.0 mA >> 3.5 mA >> 4.0 mA.

While we vary current in this protocol, other features of the stimulation will be controlled:

- **Duration of stimulation will be 30 minutes:** Data show the increased excitability of tDCS can last as long as 90 minutes. Our rehabilitation intervention will take one hour. Thus, by using 30 minutes of

stimulation, as has been commonly used in stroke studies, we should ensure that the potentially beneficial effects of the stimulation will not wear off during the course of rehabilitation.

- **Size of electrode will be 3 × 5 cm^2:** The commonly used 3 × 5 cm^2 size pad is chosen because it is adequate to cover the the primary motor cortex – our area of interest for brain stimulation in stroke subjects to facilitate upper extremity motor function recovery.

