**C2.2. Recruitment Process & Procedure:**

We will use the same study population as in Aim 1, defined by the same inclusion and exclusion criteria, for Aim 2. The same TMS, tDCS and Rehabilitation Protocols from Aim 1 will be applied to Aim 2. Those subjects who completed Aim 1 are still eligible to be enrolled in Aim 2. The subjects, therapist and assessor are all blinded to the condition.

[figure not shown]
A schedule of assessments is detailed in the following **Table 3**.

Table 3	Baseline* (Day -7 ± 7)	Session I (Day 0)		Session II (Day 2)		Session III (Day 4)	
		Pre	Post	Pre	Post	Pre	Post
Eligibility Determination and Informed Consent	X						
Demographics	X						
Vital Signs and Safety Questionnaire	X	X	X	X	X	X	X
TMS Evaluation	X	X	X	X	X	X	X

[figure not shown]
[figure not shown]
[figure not shown]
\* Baseline can be same day as Session I to facilitate recruitment.

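### In the expected course only three subjects receive 4 mA, which leaves major-response rates up to 71% not excluded; D1.3 plans no interval and D2.3 no safety summary

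*Combined protocol and SAP*

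**What the plan says.** D1.1 escalates through "1.0 mA >> 2.0 mA >> 2.5 mA >> 3.0 mA >> 3.5 mA >> 4.0 mA". Three subjects without a major response are enough to leave a level: "if no major response occurs in any of the three subjects, a next current at 2 mA will be used next". One response triggers an expansion: "if major response occurs in one subject, then 3 additional study subjects will be entered to further test the safety of same current dose". The level is then passed if the second three are free of major responses.

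D1.3 expects no major response at any level and therefore 18 subjects, within a theoretical range of 3 to 36. On analysis it says that "the safety measures will be summarized by current(dose) group with descriptive statistics". For discrete variables this means counts and percentages; no confidence interval is mentioned.

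D1.4 gives the expected conclusion: "We anticipate that 4.0 mA will be tolerable and safe both at clinical and subclinical levels, as evidenced by a lack of major responses".

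Aim 2 uses the current determined in Aim 1 and gives each subject three montages on separate days. The Appendix enrolment table plans another 18 subjects for this part. Table 3 in C2.2 has a row for "Vital Signs and Safety Questionnaire" at baseline and before and after each session. It has no MRI or laboratory row. D2.3 analyses the post/pre MEP quotient and summarises demographic and clinical characteristics. It names no safety summary.

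**The concern.** D1.4 is the only place that says what would count as evidence that 4 mA is safe, and that evidence is the absence of events. In a cohort of three, absence of events is weak evidence, and nothing planned in D1.3 would put a number on how weak.

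The conclusion has consequences. The protocol presents the study as establishing safety limits for stroke patients, D5.1 plans a manuscript on efficacy and safety by current level, and D5.4 carries the chosen current into a Phase II trial.

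Aim 2 is where most exposure at the chosen current will occur, and it holds the study's only planned repeated-session data. D3.1 considers cumulative safety problems over several sessions unlikely, yet no planned analysis looks at the data that bear on this.

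**Working it through.** **1. The plan's own sample sizes.** D1.1 has six levels. With no responses, 6 × 3 = 18; with every level expanded, 6 × 6 = 36; stopping at the first level gives 3. These match D1.3. The predicted 18 therefore means 3 subjects at 4 mA.

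**2. What a result at one level excludes.** The documents state no confidence level, so 95% is assumed. For 0 events in n, the exact (Clopper-Pearson) upper limit is 1 − α^(1/n), with α = 0.025 for a two-sided 95% interval and 0.05 for a one-sided limit.

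- 0/3, two-sided: 1 − 0.025^(1/3) = 0.708.
- 0/3, one-sided: 1 − 0.05^(1/3) = 0.632.
- 1/6, from the beta quantile with parameters 2 and 5, treating n = 6 as fixed: 0.641 two-sided, 0.582 one-sided.

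So a level passed after expansion is also poorly bounded.

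**3. What Aim 2 could add.** Assume no clinically visible major response in Aim 2 or in the three Aim 1 subjects at the chosen current.

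| Subjects at the chosen current | Two-sided upper limit | One-sided upper limit |
|---|---|---|
| Aim 1 cohort only, 0/3 | 70.8% | 63.2% |
| Aim 2 only, 0/18 | 18.5% | 15.3% |
| Combined, no overlap, 0/21 | 16.1% | 13.3% |

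C2.2 lets Aim 1 subjects enter Aim 2. If all three from the chosen-current cohort did so, there would be 18 distinct people, so the 0/18 row covers that case.

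The lower rows concern a narrower event than the first. The major response defined under D1.1 includes a new DWI lesion or decreased ADC, and Aim 2 has no MRI. What remains is second-degree burn, seizure, and discontinuation because of either.

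**4. How the algorithm behaves at one level.** Given that a level with true rate p is reached, it is passed on 0/3, or on 1/3 followed by 0/3. The probability is (1 − p)³ + 3p(1 − p)² × (1 − p)³.

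- p = 5%: 0.857 + 0.116 = 97%.
- p = 10%: 0.729 + 0.177 = 91%.
- p = 20%: 0.512 + 0.197 = 71%.
- p = one-third: 0.296 + 0.132 = 43%.

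**The case against.** D1.4 is headed as anticipated results and reads as a forecast in a grant proposal. A reader might infer that the plan contains a formal rule declaring 4 mA safe on 0/3. It does not; there is no such test or decision rule, and that point stands. It does not remove the need for an interval, because the forecast states the conclusion the investigators expect to draw.

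D1.3 does promise counts and percentages by current group, so a reader would see n = 3 and could judge the imprecision. That is fair, and it makes the missing interval a modest omission.

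The forecast refers to the study subjects, which could mean all 18 in Aim 1. For 0/18 the two-sided limit is 18.5%. But 15 of those 18 would have received lower currents, so that limit does not apply to 4 mA.

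A reader might infer that the Aim 2 safety data are thrown away. They are not. They are collected every session, the section on protection of subjects calls for a side-effect assessment after each session, and the DSMB's general duties are not restricted to part 1, although its written major-response trigger is. Only a prespecified summary is missing.

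A reader might also infer that D1.1 claims a property its algorithm lacks, since it describes the maximal tolerable dose as "the dose at which one-third of the patients experience current (dose)-limiting major side effects/response". The text offers this as the usual, arbitrary convention behind 3+3 designs and then defines the maximal tolerable current operationally, as the level before the one at which the trial stops. That is a general rationale and makes no claim about operating characteristics. Nor is the 43% in step 4 the probability of selecting an unsafe current; it applies to one level, given that it is reached.

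**Conclusion.** The point holds as a limited one about reporting. In the course the plan expects, safety at 4 mA rests on three subjects, and 0/3 leaves true major-response rates up to 71% (two-sided; 63% one-sided) not excluded. D1.3 would not show this, and D2.3 prespecifies no safety summary at the current carried forward.

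The 16% two-sided limit (13% one-sided) for 0/21 is a best case. It assumes no events and no overlap with the Aim 1 cohort at the same current, pools two montages not used in Aim 1 with one that was, and counts people who had three sessions alongside people who had one. It covers clinically visible events only. It refers to 4 mA only if Aim 1 selects that level. Any subclinical claim must rest on Aim 1.

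Figure 4 is not reproduced in the available text, so its handling of the top level could not be checked; the written algorithm gives no expansion at 4 mA after 0/3. Nothing here shows an error in the escalation rule, the Aim 1 sample size or the Aim 2 primary analysis.

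**What to change.** 1. **D1.3 and D1.4.** Report the number of subjects with a major response at each current level with an exact two-sided Clopper-Pearson 95% interval. Word the conclusion as: *no major response in n subjects at this current; rates up to x% not excluded*.

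2. **D2.3.** Add a summary of subjects with a clinically visible major response (second-degree burn, seizure, or discontinuation due to either), by montage and overall. Add a supportive combined estimate with the Aim 1 cohort at the same current, counting each person once. State beside it that it mixes montages and repeated sessions and omits the DWI/ADC component, so that any subclinical statement rests on Aim 1 alone.

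3. **D1.1, optional.** Note that the algorithm selects the highest level with 0/3 or 1/6 and does not estimate a one-third rate. Give the per-level pass probabilities, conditional on reaching the level: 97%, 91%, 71% and 43% at true rates of 5%, 10%, 20% and one-third.

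The cost is SAP wording and one extra table. No more subjects are needed and the escalation rule is unchanged. The Aim 2 table relies on burns and seizures being recorded as such at each session, which should be confirmed on the case report form. The price is a less favourable safety statement for the chosen current.

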**Aim 2: To determine the optimal stimulation montage in stroke patients**

**D2.1. Design:**

This is a repeated measures design in which a group of stroke subjects will each receive one of three stimulation montages (anodal stimulation, cathodal stimulation and bihemispheric stimulation) on three different days (separated by at least two days in between). The order in which they receive the three montages will be randomized to account for order effects. The primary purpose here is to determine the stimulation montage that induces the largest cortical excitability on the lesional hemisphere. The rationale of the design is that each subject serves as his/her own control, thus eliminating between-subject variation and makes it easier to determine changes in cortical excitability between conditions. We will require at least two days between each stimulation session so that there is little risk of carry over as the after-effect from tDCS have been shown to last over one hour.

**C2.2. Recruitment Process & Procedure:**

We will use the same study population as in Aim 1, defined by the same inclusion and exclusion criteria, for Aim 2. The same TMS, tDCS and Rehabilitation Protocols from Aim 1 will be applied to Aim 2. Those subjects who completed Aim 1 are still eligible to be enrolled in Aim 2. The subjects, therapist and assessor are all blinded to the condition.

[figure not shown]
A schedule of assessments is detailed in the following **Table 3**.

Table 3	Baseline* (Day -7 ± 7)	Session I (Day 0)		Session II (Day 2)		Session III (Day 4)	
		Pre	Post	Pre	Post	Pre	Post
Eligibility Determination and Informed Consent	X						
Demographics	X						
Vital Signs and Safety Questionnaire	X	X	X	X	X	X	X
TMS Evaluation	X	X	X	X	X	X	X

[figure not shown]
[figure not shown]
[figure not shown]
\* Baseline can be same day as Session I to facilitate recruitment.

**Baseline Day (Total Estimated Time: ~ 1.5 hour)**

1. Subject reports to the CHP building QBAR laboratory.
2. Subject gets consented first and starts screening process.
3. Demographics collected, including age, ethnicity, gender, time from stroke, side of infarct, handedness, medical history and medication list. Estimated time is 20 minutes.

- Subjects of childbearing age will have a urine pregnancy test.
- A technician from the **BSTIM Core** will perform a **Basic TMS Neurophysiological Assessment** to determine if a MEP is inducible on abductor pollicis brevis (APB) muscle on the affected side by TMS (Details in **BSTIM Core**). Estimated time is 30 minutes.
- A therapist from the **QBAR Core** will perform **Clinical Assessments** including upper-extremity Fugl-Meyer (UE-FM) scale. Estimated time is 30 minutes.
- Subjects who meet the inclusion/exclusion criteria are eligible for study and move to the next step.

### **D2.3 Statistical Analysis:**

The primary outcome measure will be the quotient of post/pre MEPs amplitude recorded from the affected APB muscle to represent the cortical excitability in the lesional motor cortex. Assuming power of 85% and type I error of 0.05, (Bonferroni adjusted for 3 comparisons), 18 subjects would be sufficient to detect an effect size of 0.85 of the MEPs between two treatments groups using a paired t-test. We will summarize the demographic and clinical characteristics of the sample using means and proportions. Although the study is powered based on paired t-tests, we will analyze the data using a repeated measures ANOVA for the post/pre MEP quotient and include covariates in the secondary analyses to glean more information about the variability in the outcome. The statistical analyses will be performed with SAS V9.2 (SAS Institute Inc., Cary NC).

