#### **Aim 2: To determine the optimal tDCS electrode montage in stroke subjects**

We hypothesize that the bi-hemispheric stimulation with anodal stimulation on the lesional hemisphere and simultaneous cathodal stimulation on the non-lesional hemisphere induces more cortical excitability in the lesional hemisphere than either anodal stimulation on the affected hemisphere or cathodal stimulation on non-lesional hemisphere alone. We will use a randomized, complete block design in which all stroke subjects undergo each of the three electrode montages (on different days) at the current determined in Aim1. As in Aim 1, MEPs from the affected APB muscle will be recorded pre- and post- stimulation to determine the optimal montage for the maximal cortical excitability from the lesional hemisphere.

This proposal lays the scientific foundation for systematic application of tDCS in stroke recovery research. It also serves as an important bridging step between the applicant's prior training and his next milestone - a Phase II single-center clinical trial (a R01 application) to assess the efficacy of tDCS for stroke motor recovery with the optimal current and stimulation montage determined by this proposal.

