### **D2.4 Anticipated Results:**

We anticipate that the bihemispheric stimulation ( anodal on the lesional hemisphere and cathodal stimulation on the non-lesional hemisphere) will induce the largest increase in the cortical excitability in the lesional hemisphere compared with the other two stimulation montages – anodal stimulation on the lesional hemisphere only or cathodal stimulation on non-lesional hemisphere only.

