**Appendix:****1. Total enrollment table**

Please refer to statistical analytic plan for sample size calculation, 36 subjects (18 subjects for part I and another 18 subjects for part II) are needed.

TARGETED/PLANNED ENROLLMENT: Number of Subjects			
Ethnic Category	Sex/Gender		
	Females	Males	Total
Hispanic or Latino	2	2	4
Not Hispanic or Latino	16	16	32
Ethnic Category: Total of All Subjects*	36		
Racial Categories			
American Indian/Alaska Native	1	1	2
Asian	1	1	2
Native Hawaiian or Other Pacific Islander	0	0	0
Black or African American	8	8	16
White	8	8	16
Racial Categories: Total of All Subjects*	18	18	36

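### Does the 85% power for 18 subjects in Aim 2 fail to match its stated inputs?

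*Combined protocol and SAP*

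**What the plan says.** The Aim 2 sample size rests on two statements in D2.3: "Assuming power of 85% and type I error of 0.05, (Bonferroni adjusted for 3 comparisons") and "18 subjects would be sufficient to detect an effect size of 0.85 of the MEPs between two treatments groups using a paired t-test". The same section separates the planning test from the analysis: "Although the study is powered based on paired t-tests, we will analyze the data using a repeated measures ANOVA for the post/pre MEP quotient". Enrolment follows the calculation without an allowance for loss; Appendix 1 states that "36 subjects (18 subjects for part I and another 18 subjects for part II) are needed".

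The hypothesis has a direction. The Aim 2 section expects that bi-hemispheric stimulation "induces more cortical excitability in the lesional hemisphere than either anodal stimulation on the affected hemisphere or cathodal stimulation on non-lesional hemisphere alone", and D2.4 expects that it "will induce the largest increase in the cortical excitability in the lesional hemisphere compared with the other two stimulation montages". No direction is given for anodal against cathodal stimulation.

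D2.3 does not state sidedness, the SD by which 0.85 is standardised, or the error term for the pairwise montage contrasts.

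**The concern.** A reader who checks the calculation will probably take the test as two-sided. Three comparisons are counted, one of them has no predicted direction, and nothing calls the tests one-sided. On that reading the stated power is not reached at 18 subjects.

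Two other matters make this look worse. The SD behind 0.85 is not named, and power is sensitive to it. The 85% also refers to one pair of montages, whereas the hypothesis sets bi-hemispheric stimulation above both others. The montage chosen here is to be carried into a Phase II trial, so an overstated power could give false assurance about that choice.

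**Working it through.** **Inputs.** From D2.3: n = 18, effect size d = 0.85, overall type I error 0.05 over 3 comparisons, power 85%. Per-comparison level: 0.05/3 = 0.01667. Assumption: d is the mean difference divided by the SD of the within-subject differences, the scale on which a paired t-test works.

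**Formula.** Power = P(T > t_crit), where T is non-central t with noncentrality d√n = 0.85 × √18 = 3.606. The opposite tail is negligible. Only the critical value and the degrees of freedom change between readings.

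| Reading, all at 0.05/3 | df | t_crit | Power at n = 18 | Smallest n for 85% |
|---|---|---|---|---|
| Two-sided contrast, pooled ANOVA error, sphericity | 34 | 2.518 | 85.5% | 18 (n = 17: 82.9%) |
| One-sided paired t | 17 | 2.316 | 89.1% | 17 (86.9%) |
| Two-sided paired t | 17 | 2.655 | 81.7% | 20 (n = 19: 84.4%; n = 20: 86.7%) |

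The pooled-error row reproduces the plan's pair of figures, 18 subjects and 85%. If period terms are fitted the error has 32 df and power is 85.3%. A simulation of 500,000 trials gave 81.7% for the two-sided paired t-test and 89.1% for the one-sided.

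**Normal approximation, two-sided.** n = ((2.394 + 1.036)/0.85)² = 16.3, so 17 subjects, with 88.7% power at 18. A planner using this shortcut would also find 18 sufficient.

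**Size of the gap on the adverse reading.** 85.0 − 81.7 = 3.3 points. In subjects, 20 − 18 = 2. In effect size, 85% at n = 18 needs d = 0.885, and 0.885 − 0.85 = 0.035.

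**Which SD.** If 0.85 were in single-session SDs, the effect on the paired scale would be 0.85/√(2(1 − r)), with r the within-subject correlation. The documents examined give no r. Over an assumed range:

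- r = 0.3: 0.718, two-sided paired power 65%
- r = 0.5: 0.850, power 82%
- r = 0.7: 1.097, power 97%

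**Choice of montage.** D2.1 gives the purpose as finding the montage with the greatest effect on the lesional hemisphere. If both bi-hemispheric contrasts have effect 0.85, the chance that either one points the right way is Φ(3.606) = 0.9998. The chance that the bi-hemispheric mean is the highest observed is then at least 1 − 2 × 0.0002 = 0.9996.

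**The case for a change.** The strongest case for a change is that no two-sided reading keeps both the paired t-test and the three-way adjustment and still reaches 85%. The pooled-error reading fits the numbers, but D2.3 names paired t-tests as its basis, so one of the two statements would be off. The arithmetic in that argument is right. It still depends on a two-sided test, which D2.3 does not specify. The section claims sufficiency, not that 18 is the minimum, and a one-sided test meets that claim.

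The SD point has substance, since the range is wide. It shows an undocumented input, not a wrong one. For a paired t-test the SD of the differences is the usual scale. Part of the text ahead of section D, next to the preliminary-data summary, is missing from the version examined, so the basis of 0.85 may be given there.

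On joint power, significance of both bi-hemispheric contrasts at two-sided 0.05/3 has a probability of about 71% if both effects are 0.85 and the two differences correlate at 0.5 (67% to 77% for correlations from 0 to 0.9). The plan sets no such both-contrasts rule, and D2.3 already presents its figure as pairwise: "detect an effect size of 0.85 of the MEPs between two treatments groups". A different multiplicity rule would be a design preference, not a correction.

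Enrolment has no slack. On the two-sided paired reading, one or two non-completers leave 78.6% or 75.1%. That is a fair remark about a small study, but it is separate from whether the stated figure is wrong. D3.1 already names a larger sample or multiple sessions as the response if differences prove smaller than expected.

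**Conclusion.** The concern does not call for a change. The stated 85% is missed only if the tests are two-sided paired t-tests, and then by 3.3 points or 2 subjects. It is met one-sided (89.1%) and on the pooled error of the planned ANOVA (85.5%, assuming sphericity). All three figures assume 0.85 is on the SD of the differences and that all 18 subjects complete.

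The missing details belong to a planning calculation. Recording them would leave the estimates, the tests and the planned enrolment as they are. An analyst would ordinarily settle sidedness and the contrast error term when programming the repeated measures ANOVA. The scale of 0.85 remains undocumented in D2.3, and a reader who wants to rely on the 85% should keep that in mind, but nothing in the documents shows it was misapplied.

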### **D3.1 Limitation, Potential Pitfall and Alternative Approach:**

- Why not perform these studies in healthy subjects first? We are pursuing a similar study in healthy subjects through other funding mechanisms. However, the information from healthy subjects can not be applied to stroke patients because they are completely different populations. In general, there is a concern for potential increased risk for stroke patients for tDCS stimulation.
- We are testing for effects and safety with a single session, but the treatment studies would likely involve multiple tDCS sessions? Feasibility, unlikely to see cumulative safety issues over multiple sessions.
- If the difference of induced cortical excitability between different electrode stimulation montage is smaller than expected, the alternative approach is to increase sample size or consider multiple sessions rather than single session.

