### **D5.4. Applicant's Future Project (Including R01):**

This proposal serves as a critic bridging step between the applicant's prior training and his next milestone - an R01 application. The R01 is planned to submit in the end of year two when the proposed experiments are close to completion. The proposed R01 project is a Phase II single-center clinical trial to assess the efficacy of tDCS for post-stroke motor recovery with the current and stimulation montage determined from this proposal. If R01 project show promising result, [name] hope to launch a U01 project to further test the tDCS in post-stroke motor recovery in a multi-center phase III clinical trial.

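### Aim 2 is powered at 85% for one pair of montages, but its hypothesis is that bihemispheric beats both others; D2.3 carries no pairwise procedure into the analysis, and the Bonferroni tests used for sizing would give only about 67–77% power for that conclusion

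*Combined protocol and SAP*

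**What the plan says.** The Aim 2 hypothesis in the Specific Aims is that bihemispheric stimulation "induces more cortical excitability in the lesional hemisphere than either anodal stimulation on the affected hemisphere or cathodal stimulation on non-lesional hemisphere alone". D2.4 repeats the expectation: bihemispheric stimulation "will induce the largest increase in the cortical excitability in the lesional hemisphere compared with the other two stimulation montages". D2.1 puts the purpose more loosely: "The primary purpose here is to determine the stimulation montage that induces the largest cortical excitability on the lesional hemisphere".

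D2.3 gives the sizing: "Assuming power of 85% and type I error of 0.05, (Bonferroni adjusted for 3 comparisons"), with the result that "18 subjects would be sufficient to detect an effect size of 0.85 of the MEPs between two treatments groups using a paired t-test". The analysis sentence then reads "Although the study is powered based on paired t-tests, we will analyze the data using a repeated measures ANOVA". The outcome is the post/pre MEP quotient, and covariates enter only in secondary analyses.

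Bonferroni appears only in the sizing sentence. No section names the contrasts that follow the ANOVA, their level, or the result that would make one montage optimal. D5.4 says that the planned Phase II trial will go ahead "with the current and stimulation montage determined from this proposal".

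**The concern.** A repeated measures ANOVA asks whether the three montages differ at all. A significant F does not say which montage is best, and it does not show that bihemispheric exceeds both others. That conclusion needs two pairwise results to succeed together, whereas the sizing covers one pair. The probability that both succeed is lower than the probability that a given one does, so 85% overstates the chance of confirming the hypothesis under the tests used for sizing.

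With the follow-up left open, the same 18 subjects could be reported as confirming or not confirming the hypothesis, depending on whether unadjusted tests, Bonferroni tests or the highest mean is chosen afterwards. The chosen montage is the one product of Aim 2 and goes into the next trial.

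**Working it through.** **Inputs from D2.3:** n = 18, effect size 0.85, type I error 0.05, three comparisons, paired t-test, stated power 85%.

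**Assumptions not in the documents:** 0.85 is the mean paired difference divided by its SD; it holds for both bihemispheric contrasts; differences are normal; there is no dropout or period effect. The correlation ρ between the two differences (bihemispheric minus anodal, bihemispheric minus cathodal) is varied from 0 to 0.9. With equal variances and equal correlations among montages, ρ = 0.5, because the covariance of the two differences is then half their variance.

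**1. The plan's own figure, one pair.** Level 0.05/3 = 0.01667; noncentrality 0.85 × √18 = 3.606; 17 df.
- Two-sided: critical t 2.655, power 81.7% (n = 19: 84.4%; n = 20: 86.7%).
- One-sided: critical t 2.316, power 89.1%; 17 subjects reach 85%.
- Two-sided contrast with the pooled ANOVA error (34 df): 85.5%.
- Normal approximation, two-sided: ((2.394 + 1.036)/0.85)² = 16.3, so 17 subjects.

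The required n runs from 17 to 20 under these readings, so 18 is consistent with the stated inputs. Sidedness and the standardiser of 0.85 are not given.

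**2. Power to beat both montages, n = 18.** Simulated with 100,000 or more trials per setting, Monte Carlo standard error at most 0.2 points. Entries are percentages.

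| Rule | ρ = 0 | 0.25 | 0.5 | 0.75 | 0.9 |
|---|---|---|---|---|---|
| Bonferroni 0.05/3, two-sided | 66.8 | 68.5 | 70.6 | 73.7 | 76.6 |
| Bonferroni 0.05/3, one-sided | 79.3 | 80.4 | 81.7 | 83.8 | 85.6 |
| Holm over three pairs, two-sided | 74.7 | 75.7 | 77.3 | 79.5 | 81.7 |
| Closed test, Hotelling first | 85.5 | 85.8 | 85.7 | 84.8 | 84.1 |
| Closed test, Greenhouse-Geisser F first | 81.7 | 84.6 | 86.7 | 88.4 | 89.9 |
| Both pairs at two-sided 0.05, no overall test | 85.6 | 86.1 | 87.0 | 88.4 | 89.9 |

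Check at ρ = 0, where the two tests are almost independent: 0.8166² = 66.7% and, from one-pair power of 92.45% at two-sided 0.05, 0.9245² = 85.5%.

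At ρ = −0.25 and −0.5 the Hotelling version stays at 85.2% and 85.0%. The Greenhouse-Geisser version falls to 77.7% and 72.2%.

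**3. Error control of the closed test.** With three means, either all are equal, which the overall test covers at 0.05, or at most one pair is equal, and that pair is tested at 0.05. Simulated family-wise error with Hotelling first was 0.047–0.051 for normal data, including unequal montage SDs. An uncorrected F first gave about 0.06 when sphericity failed, so the overall test must be Hotelling's or sphericity-corrected.

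**4. Sensitivity (ρ = 0.5; closed test with Hotelling first, against two-sided Bonferroni).**
- Both effects 0.70: 66% against 46%.
- Effects 0.85 and 0.70: 75% against 56%.
- 17 completers: 83% against 66%.
- 16 completers: 79% against 62%.

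If the quotient is lognormal and analysed raw (within-subject log correlations of 0 to 0.5 tried), the closed test falls from 84% at a log SD of 0.2 to 57–63% at 0.8. Analysed as a log quotient it stays at 86%.

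**The case against.** **The procedure is nearly there.** D2.3 names the test, the number of comparisons, the adjustment and the family-wise level. A fair reader can take it to mean three Bonferroni paired tests alongside the ANOVA. This stands in part: it would be too strong to infer that the plan has no pairwise method at all. But the analysis sentence sets the ANOVA against the t-tests and does not repeat the adjustment, and the Bonferroni reading is the one that gives 67–77%.

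**Is 18 wrong?** A reader might infer this from the 81.7%. The documents do not support it: one-sided tests or a pooled-error contrast reach 85% with 18.

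**The overall test is not needed for the stated hypothesis.** This stands. Beating both is a single joint claim, and requiring both paired tests at two-sided 0.05 controls its error unaided, with about 85–90% power. The overall test protects the other pairwise claims, for example if anodal proves best, and D2.1 asks for the best of three. For the joint claim it adds no power, and with Hotelling it costs up to 89.9 − 84.1 = 5.8 points.

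**The comparator is weak.** Also fair. Two-sided Bonferroni is the least powerful rule in the table; Holm reaches 75–82%. Against one-sided Bonferroni the closed test with Hotelling gains 6 points at ρ = 0 and loses 1.5 at ρ = 0.9.

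**Aim 2 may only be a selection.** D2.1 allows this. Under the assumptions above, bihemispheric has the highest observed mean in 99.97% of trials and no test is needed. The Specific Aims, however, state a hypothesis, and D2.3 sizes a test.

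**D3.1 already covers a small difference.** There, "the alternative approach is to increase sample size or consider multiple sessions rather than single session". That answers a true difference smaller than planned, which no decision rule can cure. It does not supply the missing rule.

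**Conclusion.** The point holds in a limited form and should be fixed before analysis. The 85% in D2.3 is power for one pair, and no pairwise procedure is carried into the analysis that would confirm or refute the Aim 2 hypothesis. With the named Bonferroni level and two-sided paired tests, power to beat both is about 67–77%. A closed test with Hotelling's T-squared first gives about 84–86% with the same 18 subjects, a gain of about 7 to 19 points.

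All these figures are conditional on the assumptions listed. Smaller effects, dropout or a right-skewed raw quotient lower them. If one-sided tests were intended, the gain is small and the main benefit is having a stated rule. The sample size itself is not shown to be in error.

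**What to change.** In D2.3, replace the Bonferroni adjustment with a closed procedure, for example:

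> The overall montage test is Hotelling's T-squared at 0.05. Only if it is significant is each of the three pairs tested at two-sided 0.05 on its own paired differences. Bihemispheric stimulation is declared superior only if it exceeds both other montages. With 18 complete subjects, approximately normal paired differences and a true difference of 0.85 SD of the paired difference from each other montage, power for this is about 84–86% (correlation 0 to 0.9 between the two differences). It is lower with smaller effects, a skewed quotient or dropout.

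Acceptable alternatives:
- A sphericity-corrected F as the overall test: about 82–90% at correlations of 0 or more, less at negative ones.
- If beating both is the only confirmatory claim, both paired tests at two-sided 0.05 with no overall test: about 85–90%.
- If Bonferroni is kept, restate two-sided power as about 82% for one pair and 67–77% for beating both.
- If the montage with the highest mean will simply be taken forward, say so and make no superiority claim.

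In the same edit, state the sidedness, what 0.85 is standardised by, and whether the quotient is analysed raw or on the log scale.

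The cost is a few sentences, with no extra subjects or visits. The downsides of the closed procedure are that no pairwise claim is possible without a significant overall test, and that pairwise 95% intervals must be labelled as unadjusted.
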